#### 5.4.4 Night Time Urinary Incontinence Episodes

For each treatment cycle, a summary table for the number and proportion of patients who experienced nighttime urinary incontinence on 0, 1, or 2 nights will be presented by treatment group for study baseline and each post-treatment visit.

#### 5.4.5 PinQ Total Score

The PinQ is a 20-item questionnaire completed prior to treatment at day1 weeks 6 and 12 post-treatment and then at the qualification for retreatment visit(s) if the patient qualifies.

For each treatment cycle, the mean raw value, mean change from study baseline, and 95% CI for the mean change from study baseline in the PinQ total score (arithmetic mean) will be summarized by treatment group for each post-treatment visit.

For BOTOX treatment cycle 1, the same ANCOVA model described in Section 5.4.1 will be used.

The 3 prespecified item scores (worry about smell [question 3], feel bad about myself [question 10], and being with friends [question 20]), these will be analyzed in the same manner as described above for the PinQ total score.

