5.10.1 Qualification for Retreatment Criteria

At each follow-up clinic visit and telephone contact from week 12 after each treatment onward, the patient's treatment response will be discussed with the patient/parent/legally authorized representative.

Patients/parents/legally authorized representatives can request retreatment at any scheduled clinic or telephone visit from week 12 onwards, or between scheduled visits. If the request is made at a scheduled clinic visit and all qualification for retreatment criteria are fulfilled, that visit then becomes a qualification for retreatment visit and the additional procedures will be performed. If the request occurs at a scheduled telephone visit or between visits, a qualification for retreatment clinic visit should be conducted within approximately 1 to

2 weeks of the request and the qualification for retreatment criteria should be assessed prior to performing any other procedures. The reason for the request will be collected.

In order to qualify for retreatment, the criteria listed below must be fulfilled at the qualification for retreatment visit:

- patient/parent/legally authorized representative requests retreatment
- patient has at least 1 daytime urinary urgency incontinence episode over the 2-day bladder diary collection period
- PVR urine volume must be < 200 mL
- at least 12 weeks have elapsed since previous treatment
- patient has not experienced a treatment-related serious adverse event at any time

Once these criteria are fulfilled, the patient is considered qualified for retreatment; this does not need to be repeated (or any of the associated qualification for retreatment procedures) if the patient does not get treated at the subsequent treatment visit or the treatment visit is delayed.

6. Response Measures and Summary of Data Collection Methods

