6.3.17 Health Outcome Measures

The PinQ is completed on day 1 prior to treatment. Both the PinQ and modified TBS are completed at weeks 6 and 12 after each treatment, and at the qualification for retreatment visit(s) (if the patient qualifies).

Questionnaires should be completed prior to the patient undergoing any procedure for any study visit and prior to study treatment and will be completed as detailed in Attachment 12.4. The same person(s) (patient or parent[s]/legally authorized representative[s]) should complete the questionnaires throughout the study where possible. For example, if the patient is able to complete the questionnaires themselves, they should complete all questionnaires themselves throughout the study. If a parent or legally authorized representative will assist or complete on the patient's behalf, then this should be done throughout the study.

The versions of the questionnaires provided in the protocol (Attachment 12.4) are samples and will be replaced with the local language questionnaire for the country where the questionnaire will be administered.

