## 2.2 Visit Windows

The target day and visit window for each post-treatment visit will be referenced to days after treatment. The visit window except for the first three and the last (Week 96) visit windows is defined as:

$[(\text{Target day of current visit} + \text{Target day of previous visit})/2 + 1]$  to  $[(\text{Target day of current visit} + \text{Target day of next visit})/2]$

The visit window for each study treatment cycle is given in the following table. If there are values from multiple visits in a given window, the value collected from the visit closest to the target day will be used to represent the window. If, instead of a single closest visit, 2 visits with values are equidistant from the target day, the value from the first of the 2 visits chronologically will be used to represent the window. For clinical laboratory variables, the last non-missing observation for that visit window will be used. This rule will be applied separately for each variable for non-missing data only. (The exception is because re-runs of laboratory variables may only involve 1 or a few variables and would thus include missing data for many variables).

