**Table 2 Analysis Visit Windows**

Visit	Target Day of the Visit a	Study Visit Window a
Screening		≤ Day -1
Treatment 1 Day 1	1	Day 1
Treatment 1 Week 2	15	Day 2 – Day 29
Treatment 1 Week 6	43	Day 30 – Day 64
Treatment 1 Week 12	85	Day 65 – Day 127
Treatment 1 Week 24	169	Day 128 – Day 211
Treatment 1 Week 36	253	Day 212 – Day 295
Treatment 1 Week 48	337	Day 296 – Day 379
Treatment 1 Week 60	421	Day 380 – Day 463
Treatment 1 Week 72	505	Day 464 – Day 547
Treatment 1 Week 84	589	Day 548 – Day 631
Treatment 1 Week 96	673	Day 632 – Day 715/Exit
Treatment X Day 1	1	Day 1
Treatment X Week Y	Repeat same as treatment 1	Repeat same as treatment 1

a Study Day is relative to the most recent treatment day.

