#### 5.4.6 Modified TBS

The TBS is single-item scale completed at weeks 6 & 12 posttreatment, at the qualification for retreatment visit(s) if the patient qualifies and at the study exit visit.

For each treatment cycle, the numbers and proportions of patients with a positive treatment response in the modified TBS, defined as either "greatly improved" or "improved", will be presented and the 95% CI of the proportion of patients with a positive treatment response will also be provided by treatment group for each post-treatment visit.

For week 12 post-treatment 1, the difference of the proportions of patients responding between the treatment groups (100 versus 25 U of BOTOX, and 50 versus 25 U of BOTOX) will be analyzed using the Cochran-Mantel-Haenszel (CMH) method controlling for baseline daytime urinary urgency incontinence episodes (a total of  $\leq 6$  episodes or  $> 6$  episodes over the 2-day diary collection period).

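### SAP 5.4.5 and 5.4.6: from the Week 24 window on, the PinQ rows (and in part the modified TBS rows) would describe patients who qualified for retreatment, not the dose group

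*SAP*

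**What the plan says.** **Collection.** Protocol 6.3.17 gives the post-treatment times for both forms: "Both the PinQ and modified TBS are completed at weeks 6 and 12 after each treatment, and at the qualification for retreatment visit(s"), followed by the condition that the patient qualifies. Protocol Table 1 marks neither form at the routine clinic visits after week 12 or at exit, and Attachment 12.4 confines the questionnaires to visits that the protocol specifies. SAP 5.4.5 has the same schedule for the PinQ: "completed prior to treatment at day1 weeks 6 and 12 post-treatment and then at the qualification for retreatment visit(s) if the patient qualifies". For the TBS, SAP 5.4.6 agrees on weeks 6 and 12 but then adds "at the qualification for retreatment visit(s) if the patient qualifies and at the study exit visit". The exit visit is not in the protocol's schedule for the TBS, and SAP 13 declares no deviations from the protocol.

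**Qualifying.** Under Protocol 5.10.1 the patient or representative must ask for retreatment, and one further criterion is that the "patient has at least 1 daytime urinary urgency incontinence episode over the 2-day bladder diary collection period".

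**Windows.** SAP 2.2 and Table 2 assign visits by days since the most recent treatment. Week 12 is Day 65 to Day 127, Week 24 is "Day 128 – Day 211", and further windows run to Week 96. No row exists for a qualification visit. When several visits fall in one window, "the value collected from the visit closest to the target day will be used to represent the window".

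**Summaries.** For each cycle, the PinQ change with its 95% CI "in the PinQ total score (arithmetic mean) will be summarized by treatment group for each post-treatment visit". The 95% CI for the proportion with a positive TBS response "will also be provided by treatment group for each post-treatment visit". Neither section limits this to weeks 6 and 12 or sets qualification values apart.

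**The concern.** A row labelled Week 24 will be read as the state of the dose group 24 weeks after treatment. If the only forms completed by then come from patients who want, and qualify for, another treatment, the row describes that subset. Membership depends on outcome, and the dose groups may differ in how many patients qualify and when, so a comparison of doses by eye in these rows is also selected on outcome.

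The diary is completed before every clinic visit. The diary tables under the same label therefore include patients who are not seeking retreatment, and the two sets of tables can disagree only because they describe different patients. Protocol 7.2.2 lists the PinQ and TBS as secondary efficacy variables, and repeated-treatment efficacy is a study objective (Protocol 2.1), so the later rows will be looked at.

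**Working it through.** **1. Reproduce the window.** SAP 2.2 uses midpoints between target days. With targets of Day 85 (Week 12), Day 169 (Week 24) and Day 253 (Week 36):
- start of Week 24: (169 + 85)/2 + 1 = 128
- end of Week 24: (169 + 253)/2 = 211

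Both agree with Table 2.

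**2. Place each questionnaire source in a window.**

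| Source | Days since treatment | Table 2 window | Who supplies a value |
|---|---|---|---|
| Week 6 visit, ±7 days | 43 ± 7 = 36 to 50 | Week 6 (30 to 64) | all who attend |
| Week 12 visit, ±7 days | 85 ± 7 = 78 to 92 | Week 12 (65 to 127) | all who attend |
| Qualification visit, Day 85 to 127 | 85 to 127 | Week 12 | normally displaced by the week 12 visit, which is closer to target; fills the window if that visit was missed |
| Qualification visit, Day 128 on | 128 and later | Week 24 and later | only patients who qualify |
| Exit visit (TBS, SAP only) | varies | varies | patients leaving the study |

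For the PinQ, the only other way into a window from Day 128 on is a week 12 visit at least 128 − 92 = 36 days beyond its allowed range. The later PinQ rows are therefore essentially all from qualifiers.

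**3. What an exit TBS would add.** A patient never retreated exits at week 96 ± 14 days, that is Day 673 ± 14 = 659 to 687, which falls in the Week 96 window (Day 632 to 715). In cycle 1, exit forms in the Week 24 to Week 84 windows would therefore come only from patients leaving early. In later cycles exit can fall in any window. As an assumed example, a last treatment at study week 60 and exit at week 96 is 36 weeks later, Day 36 × 7 + 1 = 253, in the Week 36 window of that cycle. Exit forms would thus bring in patients who did not qualify, mixed in the same row with those who did.

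**4. Size of the shift.** The documents give neither the share q of patients in a window who qualify nor the correlation ρ between the tendency to qualify and PinQ change. If both quantities are assumed jointly normal, the qualifiers' mean differs from the mean of all patients in the window by ρ × φ(z)/q standard deviations, with z the (1 − q) normal quantile and φ the normal density.

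| q (assumed) | ρ (assumed) | Shift toward less improvement |
|---|---|---|
| 0.8 | 0.2 | 0.07 SD |
| 0.3 | 0.4 | 0.46 SD |
| 0.1 | 0.8 | 1.40 SD |
| any | 0 | 0 |

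**5. How much benefit a qualifier can retain.** Entry requires at least 2 daytime urgency incontinence episodes in 2 days; qualifying requires at least 1. Assume that all episodes are urgency incontinence and that daytime lengths are equal. A patient with 1 episode then has a reduction of 1 − 1/b from a baseline of b: 50% for b = 2, 75% for b = 4 and 83% for b = 6. All meet the 50% responder threshold in SAP 5.3.1.

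**The case against.** Four points can be made for the plan.

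*The rows are descriptive.* The PinQ ANCOVA (the SAP 5.4.1 model) covers comparisons up to week 12 of cycle 1, and the TBS Cochran-Mantel-Haenszel test is at week 12 of cycle 1 only. Descriptive statistics include n (SAP 2.3), so thin rows will be visible. This stands and limits the harm. A small n does not, however, tell the reader that the patients were selected on outcome.

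*The phrase about each post-treatment visit may mean each visit at which the form is collected.* Both SAP sections state the collection schedule just before it, and SAP 8 reports immunogenicity by collection event. The reading is fair, but it does not settle the matter, because Table 2 offers a qualification-visit value no place other than a week window.

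*Duration of effect is handled elsewhere.* A reader might infer that a longer-acting dose goes uncredited. It does not: SAP 5.5.1 estimates time to request and time to qualification by Kaplan-Meier for each dose and cycle, with patients who did not request retreatment censored.

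*Late TBS rows may not be purely qualifiers.* This is right if the SAP's exit visit was carried out, and it is why the point is complete for the PinQ but only partial for the TBS.

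**Conclusion.** The point holds for descriptive late-visit rows. If the SAP is followed as written, PinQ summaries from Day 128 of a cycle rest essentially on patients who requested and qualified for retreatment, under labels that suggest the whole dose group. The same is true of the TBS under the protocol's schedule, and partly true under the SAP's. Persisting benefit is probably understated. The direction assumes that patients who qualify have, on average, improved less on the PinQ than those who do not. The range in the working illustrates possible sizes and is not an estimate.

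A reader might go further and infer that these tables will show the benefit as lost, or that everyone in them has relapsed. The documents do not support that. Qualifying is possible with a reduction of 50% or more in episodes, and the TBS asks for comparison with the condition before any study treatment, so a partial benefit can still be rated as improved. Whether the benefit would look lost depends on the true mean change, which the documents do not give.

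The primary endpoint, the diary endpoints and the week 12 PinQ and TBS comparisons do not have this gap.

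**What to change.** In SAP 5.4.5 and 5.4.6:
- Limit the by-visit PinQ and TBS summaries to weeks 6 and 12 of each cycle. This matches Protocol 7.3.3.2 for cycle 1. It also settles the looser references to post-treatment visits in Protocol 7.3.3.7 and in the protocol summary's text on the TBS.
- Show qualification-visit values in a separate row, *At qualification for retreatment*, with n, not mapped to Table 2 windows, and with a note that these are selected patients. Where the week 12 visit is itself the qualification visit, the form is completed once (Protocol Table 1, footnote g), and the SAP should say that the value counts in both rows.
- Reconcile the TBS exit visit between SAP 5.4.6 and Protocol Table 1 and 6.3.17. If the form was collected at exit, keep it and show it as its own row; it is the only late TBS source that does not require qualifying. If the visit stays in the SAP, record it in SAP 13.

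The cost is SAP wording and table shells, with no new data. The sparse late-visit rows are lost.

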#### 5.4.6 Modified TBS

The TBS is single-item scale completed at weeks 6 & 12 posttreatment, at the qualification for retreatment visit(s) if the patient qualifies and at the study exit visit.

For each treatment cycle, the numbers and proportions of patients with a positive treatment response in the modified TBS, defined as either "greatly improved" or "improved", will be presented and the 95% CI of the proportion of patients with a positive treatment response will also be provided by treatment group for each post-treatment visit.

For week 12 post-treatment 1, the difference of the proportions of patients responding between the treatment groups (100 versus 25 U of BOTOX, and 50 versus 25 U of BOTOX) will be analyzed using the Cochran-Mantel-Haenszel (CMH) method controlling for baseline daytime urinary urgency incontinence episodes (a total of  $\leq 6$  episodes or  $> 6$  episodes over the 2-day diary collection period).

## 5.5 Other Efficacy Analyses

### 5.5.1 Duration of Effect

Duration of treatment effect will be evaluated by BOTOX treatment group for each treatment cycle in 2 different ways:

- Time between a treatment and patient's first request for subsequent treatment
- Time between a treatment and qualification for subsequent treatment

Patients who did not request retreatment will be treated as censored at the time of their last study visit or study exit.

The time from the day of each BOTOX treatment to the request for the subsequent treatment will be estimated using a Kaplan-Meier survival method for each treatment group for each treatment cycle. The median duration in days (and in weeks) will be presented.

Analysis for time to qualification will be performed and presented in the same manner as described for time to request for retreatment.

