5.9 Treatment Administration

5.9.1 Day of Treatment Criteria

Administration of the first study treatment should occur within 28 days of the start of the screening procedures. For patients who request retreatment, study treatment will be administered within 4 weeks of qualification for retreatment (see Section 5.10.1 for qualification for retreatment criteria), but no later than 96 weeks since study enrollment on day 1 of this study. The following “day of treatment criteria” must be fulfilled prior to the administration of study medication:

- central laboratory urine analysis results and, if applicable, urine culture and sensitivity results for possible UTI have been reviewed
- negative urine dipstick reagent strip test (for nitrites and leukocyte esterase) on the day of treatment
- patient is asymptomatic for a UTI on the day of treatment, in the opinion of the investigator
- appropriate prophylactic antibiotics have been initiated (see Section 5.9.2)
- antiplatelet or anticoagulant therapy or medications with anticoagulative effects have been discontinued at least 3 days prior to treatment
- negative urine pregnancy result (for postmenarche females)
- for patients who request retreatment, PVR urine volume confirmed to be < 200 mL at the qualification for treatment visit
- investigator continues to deem treatment is appropriate and no condition or situation exists which, in the investigators opinion, puts the patient at significant risk from receiving treatment

Note: If a patient does not fulfill the “day of treatment criteria” they would still be considered qualified for retreatment (ie, qualification for retreatment or any associated procedures are not to be repeated). The treatment administration visit would be rescheduled for as soon as possible (if applicable), and the “day of treatment criteria” would need to be fulfilled prior to treatment administration.

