7.3.3.9 Duration of Effect

Duration of treatment effect will be assessed as time from each study drug administration to a) request for retreatment and b) qualification for retreatment using a Kaplan-Meier survival

analysis. The time from the day of each BOTOX treatment to the request for the subsequent treatment will be estimated using the Kaplan-Meier survival method for each treatment group for each BOTOX treatment cycle. For those patients who did not request retreatment, their data will be censored using the date of their last study visit or study exit. The proportions of patients/parents/legally authorized representatives requesting retreatment in each BOTOX treatment cycle will also be presented. In addition, time to qualification for retreatment will be presented and analyzed as described above for time to request for retreatment.

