#### **3.3 Study Duration**

Patients will participate in the study for at least 96 weeks following entry into the study and should have at least 12 weeks follow-up since the last treatment prior to exiting the study. The minimum duration is therefore 96 weeks, and the maximum duration is approximately 108 weeks (for patients who received their last treatment at week 96 with 12 weeks posttreatment follow-up). Thus, patients could receive a maximum of 8 BOTOX treatment cycles. For details on how to analyze duration of exposure to study treatment see Section [6.1.1](#).

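### Per-cycle Kaplan-Meier medians for duration of effect are not comparable across treatment cycles, because entry to and follow-up in cycles 2 onward depend on the same patient's earlier durations

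*SAP*

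**What the plan says.** SAP 5.5.1 defines duration of effect as time from a treatment to the first request for the next one and, separately, to qualification for it. Time to request "will be estimated using a Kaplan-Meier survival method for each treatment group for each treatment cycle". Protocol 7.3.3.9 plans the same: "estimated using the Kaplan-Meier survival method for each treatment group for each BOTOX treatment cycle". On censoring, the SAP says: "Patients who did not request retreatment will be treated as censored at the time of their last study visit or study exit". On reporting: "The median duration in days (and in weeks) will be presented".

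The cycles run on one clock. Protocol 5.10.1 requires 12 weeks between treatments. Protocol 5.9.1 allows retreatment "but no later than 96 weeks since study enrollment on day 1 of this study". SAP 3.3 gives the total follow-up ("Patients will participate in the study for at least 96 weeks following entry into the study"), adds that "the maximum duration is approximately 108 weeks", and notes that "patients could receive a maximum of 8 BOTOX treatment cycles".

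SAP 2.1 assigns each patient, in each cycle, to the dose received in that cycle. Protocol 5.5 lets the investigator raise the dose after an insufficient response. Neither document links a patient's cycles in a model or cautions against comparing medians across cycles.

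**The concern.** The start week of a later cycle is the sum of the patient's earlier durations plus the delays before each injection. Patients with long durations reach later cycles late, with little follow-up left, or never reach them. The patients in cycle 3 or 4 are therefore a selected group. Among them, those with long durations tend to be censored soonest. Kaplan-Meier assumes that censoring is unrelated to the time being estimated.

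Protocol 2.1 makes repeated treatment an objective, and protocol 6.1.2 lists time to request and to qualification as secondary measures. A reader who sees a row of medians by cycle may take it as evidence on whether the effect lasts as long with repeat treatment. A fall could be an artefact of the shared clock. Comparisons between doses in later cycles are exposed to the same problem.

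**Working it through.** **Inputs from the documents.** Minimum gap 12 weeks (protocol 5.10.1). Last retreatment at week 96 (protocol 5.9.1). Exit at the later of week 96 and last treatment plus 12 weeks (SAP 3.3). Adult duration about 6 months (protocol section 1), used here as 26 weeks. The plan states no expected duration per cycle, so there is no such figure to reproduce. Its maximum study duration does reproduce: 96 + 12 = 108 weeks.

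**Follow-up left in a cycle.** For a cycle started at week s, time left = max(96, s + 12) − s. It is 96 weeks in cycle 1 (s = 0). The earliest start of cycle k is week 12(k − 1), so at most 84 weeks remain in cycle 2, 60 in cycle 4 and 12 in cycle 8.

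**By hand.** Take three assumed patients whose durations never change: 16, 26 and 36 weeks, each with 3 weeks from request to injection.
- Cycle 2 starts at weeks 19, 29 and 39. All three requests are seen. Median 26, as in cycle 1.
- Cycle 3 starts at weeks 38, 58 and 78. The third patient has 96 − 78 = 18 weeks left and is censored there.
- Cycle 4 starts at weeks 57 and 87. The third patient never enters. The second is censored at 12 weeks. The only event is at 16 weeks, so the median is 16.

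**Simulation.** 200,000 patients per setting, with the same true duration distribution in every cycle. Assumptions not in the documents: lognormal durations, median 26 weeks, log-SD 0.6, floor 12 weeks; 3-week lag; no dropout; ICC (share of the variance of log duration that lies between patients) as shown. Kaplan-Meier medians in weeks, all doses together:

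| ICC | Cycle 1 | Cycle 2 | Cycle 3 | Cycle 4 |
|---|---|---|---|---|
| 0.3 | 26.0 | 25.7 | 23.7 | 21.0 |
| 0.5 | 26.0 | 25.4 | 22.6 | 19.0 |
| 0.7 | 26.0 | 25.3 | 21.6 | 17.7 |

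At ICC 0 the medians stay at 26 to 27 weeks.

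**Splitting the fall.** At ICC 0.5 the true median of the patients who enter cycle 4 is 20.0 weeks. The fall is 26.0 − 19.0 = 7.0 weeks. Selection into the cycle accounts for 26.0 − 20.0 = 6.0, and dependent censoring for 20.0 − 19.0 = 1.0.

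**A second duration model.** With 12 weeks plus a lognormal time (log-SD 0.8), a lag of 1 to 5 weeks and ICC 0.5, the medians are 26.0, 25.6, 23.4 and 20.2. The true medians of entrants are 26.0, 25.9, 24.6 and 22.0. Of the 5.8-week fall, 4.0 is selection and 1.8 is censoring. With 36 patients per group, 0.3% dropout per week and no dose switching, the cycle 4 median is below the cycle 1 median in 91% of simulated trials, against 47% at ICC 0.

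**Dose switching.** In the second model, let patients who request before week 22 escalate with probability 0.8, and give dose no effect. The group that stays on its starting dose then shows 26.0, 27.9, 26.3 and 21.7: it rises before it falls.

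**Contrast between durations.** In the first model at ICC 0.5, true medians of 20 and 32 weeks, 12 apart, give cycle 4 medians of 16.7 and 20.7, 4 apart.

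**The case against.** The strongest reply is that the medians are descriptive. No test or stated comparison across cycles is planned, and the primary analysis is untouched. Disposition by cycle (SAP 3.2) and follow-up by cycle (SAP 6.1.1) will already show how many patients enter and how long they stay. Cycle 2, the best populated repeat cycle, moves by less than 1 week in the table above. All of this stands, and it limits the weight of the point. It does not remove it: those tables show that numbers shrink, not that the remaining patients are selected on duration.

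Four stronger readings are tempting, and the documents support none of them.
- **The table shows waning by construction.** It does not. The fall needs durations that correlate within a patient, and neither document gives that correlation.
- **Shrinking follow-up is the main cause.** In both models most of the fall is who enters the cycle.
- **Every printed median must fall.** Groups are formed by the dose received in each cycle, and escalating short responders can raise the median of the dose they leave.
- **A cycle started at week 84 or later can never show an event.** The week 96 limit is on giving treatment, whereas the event in SAP 5.5.1 is a request. Protocol Table 1 collects the reason for a request at week 12 of retreatment cycles, and nothing bars recording one then.

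**Conclusion.** The point holds as one of comparability and labelling. From cycle 2 onward each curve describes patients selected on their own earlier durations, with follow-up that depends on those durations. The plan neither corrects for this nor warns of it.

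The size rests on the assumed ICC and on the other stated assumptions. For ICC 0.3 to 0.7, medians over all doses with no true change are about 26, 25.5, 22 to 24 and 18 to 21 weeks in cycles 1 to 4. At ICC 0 there is no fall. Medians for single dose groups may rise or fall, which is a further reason not to compare them.

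Cycle 1 does not have this problem, because every patient enters it on day 1. The SAP amendment log says recruitment was stopped early, so groups may be smaller than the planned 36 and late medians less stable. This is a worthwhile, cheap improvement to a secondary, descriptive analysis.

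**What to change.** In SAP 5.5.1:
1. Keep Kaplan-Meier for cycle 1 and name it as the estimate of duration of effect.
2. Label the curves for cycles 2 onward as conditional on entering that cycle and not comparable across cycles. Print the numbers entering and censored beside each median.
3. Add the mean cumulative number of retreatment requests per patient from day 1 to week 96, by dose group at treatment 1, with robust variance. It follows every treated patient from day 1 and so avoids selection into cycles. It describes the starting dose with any later escalation, not a fixed dose. State how early exits are handled, since some exits required by protocol 5.5 follow from response or side effects.
4. If change across cycles is to be assessed, use a gap-time model with a patient random effect and cycle and dose terms. In 8,000 patients simulated from the second model at ICC 0.5, a random-effect model with cycle terms gave 25.9, 25.8, 25.9 and 26.0 weeks for cycles 1 to 4. Per-cycle Kaplan-Meier on the same data gave 25.8, 25.3, 23.4 and 20.2. That is a best case, because the model form matched the simulation.

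Do not restrict later cycles to those started by week 48. This removes the early censoring but strengthens the selection. In the first model at ICC 0.5 the medians become 23.8, 17.6 and 12.0 in cycles 2 to 4, with about 31% of patients left in cycle 3 and 4% in cycle 4.

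Cost: SAP wording and one extra summary from dates already collected, plus the model if it is wanted. The later-cycle medians become descriptive only.
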